8.2. Efficacy Assessments

Planned timepoints for all efficacy assessments are provided in the SoA.

Screening and subsequent tumor assessments must include CT scans (with IV contrast unless contraindicated and oral contrast as appropriate per institutional standards) of the head and neck, chest, abdomen, pelvis and other site of disease for sarcoma as needed. If a CT scan for tumor assessment is performed in a positron emission tomography (PET)/CT scanner, the CT acquisition must be consistent with the standards for a full-contrast CT scan. Brain imaging (either MRI or contrast-enhanced CT) is required at screening for all subjects. Further investigations such as bone scans and CT scans of the neck should also be performed if there is any clinical suspicion of disease at any site that may not be demonstrated by the minimum schedule of assessments listed above. At the investigator's discretion, other methods of assessment of measurable disease as per RECIST v1.1 may be used.

The same radiographic procedures used to assess disease sites at screening should be used throughout the study (eg, the same contrast protocol for CT scans). Response will be assessed by the investigator on the basis of physical examinations and the imaging modalities detailed above, using RECIST criteria. Assessments should be performed by the same evaluator, if possible, to ensure internal consistency across visits.

Tumor assessments will be performed every 8 (± 1) weeks from Cycle 1 Day 1 through Week 48 and then at least every 12 (± 1) weeks or as clinically indicated until confirmed progression of disease (as defined below), alternate anticancer therapy, withdrawal of consent, or death, whichever occurs first. The radiographic assessments are to be conducted as noted, independent of dose delays and/or dose interruptions. RECIST 1.1 criteria will be used for primary endpoint evaluation ([Eisenhauer et al., 2009](#)), iRECIST will be used for exploratory endpoint response evaluation ([Seymour et al., 2017](#)).

Response assessment data (ie, progressive disease or no progression of disease) will continue to be collected (based on standard-of-care radiographs) for subjects who have not progressed at the time of the termination visit, until the subject starts alternative anti-cancer treatment or develops progressive disease, whichever occurs first. Response assessment and assessment of tumor markers will be obtained at treatment termination, unless a prior radiographic assessment has been performed within the last 14 days or at a prior response assessment that documented progressive disease. At the investigator's discretion, scans may be performed at any time if progressive disease is suspected.

8.3. Safety

Planned timepoints for all safety assessments are provided in the SoA.

8.3.1. Adverse Events

Measures will be taken to ensure the safety of subjects participating in this trial, including the use of stringent inclusion and exclusion criteria (see [Section 3.1](#) and [Section 3.2](#)) and close monitoring. All subjects will be monitored closely for toxicity. Administration of etigilimab and nivolumab will be performed in a setting with available emergency medical facilities with access to a critical care unit and staff who are trained to monitor for and respond to medical emergencies.

The definitions of an AE or SAE can be found in [Appendix 4](#). Management guidelines for specific AEs can be found in [Appendix 8](#).

AE will be reported by the subject (or, when appropriate, by a caregiver, surrogate, or the subject's legally authorized representative).

The investigator and any designees are responsible for detecting, documenting, and reporting events that meet the definition of an AE or SAE and remain responsible for following up AE that are serious, considered related to the study treatment or the study, or that caused the subject to discontinue the study treatment.

8.3.1.1 Time Period and Frequency for Collecting AE and SAE Information

All AEs will be collected from the start of treatment with etigilimab until 90 days after the treatment termination visit and at the timepoints specified in the SoA. SAEs will be collected starting after signature of the informed consent until 90 days after the treatment termination visit.

Medical occurrences that begin before the start of study treatment but after obtaining informed consent will be recorded on the Medical History/Current Medical Conditions section of the case report form (CRF).

All SAEs will be recorded and reported to the sponsor or designee within 24 hours, as indicated in [Appendix 4](#). The investigator will submit any updated SAE data to the sponsor within 24 hours of it being available.

Investigators are not obligated to actively seek AE or SAE information in former study subjects. However, if the investigator learns of any SAE, including a death, at any time after a subject has been discharged from the study, and he/she considers the event to be reasonably related to the study treatment or study participation, the investigator must promptly notify the sponsor.

The method of recording, evaluating, and assessing causality of AE and SAE and the procedures for completing and transmitting SAE reports are provided in [Appendix 4](#).

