4.2. Treatment Discontinuation

Treatment discontinuation occurs when a subject is no longer receiving study drug(s).

Note that treatment discontinuation is not the same as study withdrawal. A subject should be discontinued from study treatment if, in the opinion of the investigator, it is medically necessary, or if it is the wish of the subject. All subjects who discontinue study treatment should enter safety follow-up followed by survival follow-up; if a subject discontinues study treatment prior to confirmed progression of disease, the subject will continue to be followed for disease progression as per the planned study visits and procedures.

Subjects will be discontinued from study treatment for any the following reasons:

- An AE that requires permanent discontinuation of study drug(s).
- Confirmed progression of disease (Note: subjects may continue treatment beyond RECIST v1.1 determined PD).
- Noncompliance with protocol.
- Investigator decision.
- Subject becomes pregnant.
- Subject death.
- Subject lost to follow-up.
- Termination of the study by the sponsor.
- Voluntary withdrawal from the study treatment by the subject.

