7. PERMANENT AND TEMPORARY DISCONTINUATION CRITERIA

In the absence of unacceptable toxicities or disease progression, subjects will be offered continued study treatment up until disease progression. Regardless of discontinuation of study drug, subjects should continue on study with regular follow-up. All subjects who have discontinued etigilimab and nivolumab will return to the clinic for a treatment termination visit within 30 days after the last dose of etigilimab study treatment or nivolumab, whichever occurs last).

Subjects may withdraw or be withdrawn from the study at any time.

Subjects will be withdrawn from the study treatment for the following reasons:

- Clinically significant disease progression, as assessed by the investigator.
- Intercurrent illness that prevents further administration of treatment.
- Unacceptable AEs.
- Dose delay due to drug-related toxicity >28 days.
- Non-protocol anti-cancer therapy.
- Subject decides to withdraw from the study.
- General or specific changes in the subject's condition render further treatment unacceptable for the subject in the judgment of the investigator.
- Protocol non-compliance.

In the absence of progressive disease and additional anti-cancer therapy, all attempts should be made to continue tumor assessments per RECIST criteria until disease progression or initiation of subsequent anti-cancer therapy for up to 2 years.

All subjects will undergo the treatment termination evaluations.

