- k. Etigilimab must be dosed as described in the Protocol. Dosing of etigilimab should be within ± 2 days of the Study Day listed in the schedule of assessments. If etigilimab cannot be administered in this 2-day window, then that dose is considered missed. If treatment with etigilimab is delayed for >4 weeks, etigilimab will be permanently discontinued.
- l. Nivolumab must be dosed as described in the Protocol within ± 2 days of the Study Day listed in the schedule of assessments. If the etigilimab dose is delayed ± 2 days then the nivolumab dose would be delayed and administered on the same day as the etigilimab (except for C1D1 where etigilimab is administered without nivolumab).
- m. After initiation of study drug, report all adverse events until 90 days after the treatment termination visit.
- n. Thyroid function tests (TSH, free T3, and free T4) must be performed every 8 weeks or as clinically indicated and at treatment termination.
- o. Urinalysis (specific gravity, pH, glucose, protein, ketones, and blood) will be obtained during screening, at Study Days 22, 64, and at the time of treatment termination. Microanalysis is required if protein or blood is detected.
- p. Serum pregnancy test (for women of childbearing potential, including women who have had a tubal ligation) must be performed and documented as negative within 7 days prior to Cycle 1, Day 1 and at treatment termination.
- q. Perform tests for pertinent tumor markers (e.g., CEA for subjects with colorectal cancer or others) every 4 weeks or as needed starting at Cycle 1 Day 1.
- r. PK and ADA samples will be drawn according to [Table 3](#) listed below.

- s. A pre-dose sample of 33 mL will be drawn during screening and on Study Days, 1, 8, 22, and 36 and every 6 weeks after day 36 for subjects continuing on study drug to evaluate changes in plasma proteins (8 mL) by immunochemistry, TIGIT and immune-related gene expression by mRNA (5 mL) and changes in peripheral blood mononuclear cell (PBMC, 20 mL) populations and activation. A sample will also be collected at the time of treatment termination, unless one has been obtained during the prior 14 days. Instructions for the collection, handling, storage, and shipment are provided in the Laboratory Manual.
- t. A 6 mL of blood will be collected for pharmacogenetic testing if the subject has consented to have this optional sample collected.

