- w. At Cycle 7 and beyond, safety laboratory testing is completed every two weeks at each treatment visit only.
- x. The termination visit should be done as soon as possible, but no later than 30 days, after one of the discontinuation criteria for the study are met (See Protocol). The termination visit may occur later after discussion with the Sponsor Medical Monitor for specific circumstances, such as prolonged hospitalization. The visit at which a tumor assessment shows progressive disease may be used as the treatment termination visit provided that all required assessments were performed as outlined in the Schedule of Assessments. Tumor assessments do not have to be repeated if they were performed within 14 days of the termination visit or at a prior response evaluation that documented progressive disease. ECG does not have to be repeated if they were performed within 14 days of the termination visit.

Table 3 Phase 1b Subjects: PK and ADA Sample Collection Schedule

Cycle		Cycle 1	Cycle 2	Cycle 3	Cycle 4	Cycle 5	Cycle 6	Cycle 7	Cycle 8	Cycle 9	Cycle 10	Cycle 11	Treatment Termination	4 Week Post Termination
Visit Day		Day 1	Day 15	Day 29	Day 43	Day 57	Day 71	Day 85	Day 99	Day 113	Day 127	Day 141		
MPH313 Infusion		X	X	X	X	X	X	X	X	X	X	X		
PK	On Day												X	X
	Pre-Infusion	X	X	X	X	X	X	X	X	X	X	X		
	15 Minutes Post Infusion	X			X		X							
ADA	Pre-Infusion	X		X		X		X		X		X	X	X

Abbreviations: ADA = anti-drug antibody; AE = adverse event; PK = pharmacokinetics

PK will be drawn pre-infusion every cycle of etigilimab until treatment termination. ADA will be drawn pre-infusion every other cycle of etigilimab through the first 6 months of treatment. After 6 months, ADA will be collected pre-infusion every 3 months and then once every 6 months after the first year until treatment termination. Should any immune-related AE continue beyond the 4-week post treatment termination visit, a blood sample for PK and ADA may be requested by the Medical Monitor.

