9.3.2. Safety Analyses

Adverse events will be coded using the Medical Dictionary for Regulatory Activities (MedDRA) version 18.0 or higher and will be graded according to the NCI-CTCAE, v 4.03 or higher.

Summaries of AEs will be based on TEAEs. A TEAE is an AE that emerges or worsens in the period from the first dose of study treatment etigilimab or nivolumab, whichever is earlier, to 100 days after the last dose of etigilimab or nivolumab (whichever is dosed last) or until starting another treatment.

TEAEs will be summarized by treatment group and by the frequency of subjects experiencing TEAEs corresponding to MedDRA system organ classes and preferred terms.

Separate tabulations will also be produced for TEAEs assessed as related to study drug(s), TEAEs that led to treatment discontinuation, TEAEs that led to death, and TEAEs \geq Grade 3 in severity. Treatment-emergent serious AEs and SAEs related to study drug(s) will also be tabulated.

Laboratory results (hematology, serum or plasma chemistry, and coagulation) and the corresponding change from baseline values will be summarized by group and scheduled timepoint. A shift table, tabulation for baseline to each scheduled assessment and the worst post treatment value according to the CTCAE grade, will be provided for selected clinical laboratory tests. Laboratory results together with the normal ranges and CTCAE grade will be listed. Laboratory values that are below or above the normal ranges will be flagged.

Vital signs and ECGs and the corresponding changes from baseline will be summarized by group and scheduled timepoint.

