Follow-up period	All subjects who have discontinued study drug treatment will return to the clinic for a treatment termination visit within 30 days after the last dose of etigilimab or nivolumab, whichever occurs last. Following etigilimab and nivolumab study treatment discontinuation, all subjects will be followed for survival and subsequent anti-cancer therapy via telephone calls, subject medical records, and/or clinic visits approximately every 3 months until death, loss to follow-up, or study termination by the sponsor unless the subject requests to be withdrawn from follow-up.		
Number of subjects:	Screened: 135	Enrolled: 125	Completed: 115
Planned number of sites:	20 (10 in US, 5 in UK and 5 in Spain)		

Planned Subject Population for Study

Inclusion Criteria	

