10.11. Safety Analysis

All analyses of safety endpoints will be descriptive and will use the Safety Analysis Set. No formal statistical analysis of safety data will be performed.

10.11.1. *Adverse Events*

Adverse event (AE) data presentations will be produced for adverse events that occur during the study.

All adverse events will be coded using MedDRA, Version 26.0.

An adverse event is defined as treatment emergent if the onset date is on or after the date of first dose of study drug up to 100 days after the last dose of study drug and before starting any subsequent cancer treatment. Should any onset date for an adverse event be missing or only a partial date recorded (such that it cannot be determined if the event onset was prior to the date of first dose) then it will be assumed that the event is treatment emergent, unless the adverse event stop date indicates otherwise. Any adverse event with an onset date earlier than the date of first dose of study drug will be classified as a pre-treatment adverse event and will be identified in subject listings only.

A summary of treatment-emergent AEs will be presented by cohort showing the number of subjects with events (also split by severity; mild, moderate, severe), number of subjects with SAEs, number of subjects with related events and number of subjects with events leading to early withdrawal from the study.

Additionally, each of the summaries below will be presented for treatment emergent AEs:

- Adverse Events by cohort, System Organ Class (SOC) and Preferred Term (PT).
- Adverse Events by cohort, SOC, PT and severity.
- Adverse Events related to study drug by cohort, SOC and PT:
 - etigilimab
 - nivolumab
 - etigilimab and nivolumab
 - etigilimab or nivolumab
- Serious Adverse Events by cohort, SOC and PT.
- Serious Adverse Events related to study drug by cohort, SOC and PT:
 - etigilimab
 - nivolumab
 - etigilimab and nivolumab
 - etigilimab or nivolumab
- Adverse Events that led to death by cohort, SOC and PT.
- Adverse Events that led to treatment discontinuation by cohort, SOC and PT.
- Adverse Events that led to withdrawal from the study by cohort, SOC and PT.
- Adverse Events of Grade 3 or Higher by cohort, SOC and PT.
- Adverse Events of Special Interest by cohort, SOC and PT:

- Infusion Related Adverse Events
- Immune Related Adverse Events
- Infusion or Immune Related Adverse Events

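### AEs are collected to 90 days after the termination visit but TEAEs are counted to 100 days after last dose, so a termination visit within 9 days of last dose leaves 1 to 10 days uncovered

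*Protocol*

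**What the plan says.** **Collection.** Protocol Section 8.3.1.1 sets the rule: "All AEs will be collected from the start of treatment with etigilimab until 90 days after the treatment termination visit". SAE collection starts earlier, at consent, but ends at the same point. Note m to the Schedule of Assessments (Section 8.1) repeats it: "After initiation of study drug, report all adverse events until 90 days after the treatment termination visit". Section 4.6 uses a matching 90-day limit for concomitant medications.

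**Analysis.** Protocol Section 9.3.2 ends the TEAE window at "100 days after the last dose of etigilimab or nivolumab (whichever is dosed last) or until starting another treatment". SAP Section 10.11.1 has "up to 100 days after the last dose of study drug and before starting any subsequent cancer treatment". The SAP adds a second summary that keeps the 100 days but ignores subsequent cancer treatment (Sections 10.11.1 and 11). SAP Section 11 lists the changes from the protocol analysis and does not mention the difference between the collection and analysis windows.

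**The visit that anchors collection.** Section 7 says that subjects who have stopped both drugs "will return to the clinic for a treatment termination visit within 30 days after the last dose", and the synopsis agrees. Schedule note x reads: "The termination visit should be done as soon as possible, but no later than 30 days, after one of the discontinuation criteria" being met. It allows a later visit after discussion with the Medical Monitor, and lets a visit that shows progression serve as the termination visit.

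**After termination.** Section 4.2 says: "All subjects who discontinue study treatment should enter safety follow-up followed by survival follow-up". The synopsis describes the later contacts: "all subjects will be followed for survival and subsequent anti-cancer therapy via telephone calls, subject medical records, and/or clinic visits approximately every 3 months".

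**The concern.** Collection is tied to a visit whose timing can vary, and the analysis is tied to the last dose. When the visit comes soon after the last dose, collection can close before the analysis window does. The tables then report events to Day 100 in subjects whose sites had no duty to collect them that far. Events in that gap can only be missed, and the length of ascertainment differs between subjects in a way that no table shows.

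The outputs at stake are the TEAE, SAE and AESI summaries. AESIs (infusion reactions and immune-related AEs) are a named secondary endpoint, and immune-related events can begin after treatment has stopped.

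**Working it through.** **Inputs.** Collection ends at the termination visit + 90 days (Section 8.3.1.1, note m). The TEAE window ends at last dose + 100 days (Section 9.3.2, SAP Section 10.11.1). The documents give no derived figure to reproduce.

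**Formula.** Let t be the number of days from the last dose of either drug to the termination visit.

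- Collection ends on day t + 90.
- Uncovered days = 100 − (t + 90) = 10 − t when t < 10, and none otherwise.
- Days collected beyond the TEAE window = t − 10 when t > 10.

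| t | Collection ends (day after last dose) | Uncovered days | Days beyond window |
|---|---|---|---|
| 0 | 90 | 10 | 0 |
| 3 | 93 | 7 | 0 |
| 5 | 95 | 5 | 0 |
| 7 | 97 | 3 | 0 |
| 9 | 99 | 1 | 0 |
| 10 | 100 | 0 | 0 |
| 14 | 104 | 0 | 4 |
| 30 | 120 | 0 | 20 |

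**Can t be below 10 under the schedule?** Yes, by several routes:

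- An abrupt stop for an AE on a dosing day, with the visit done at once: t = 0.
- A stop at the Day 8 visit of a cycle: 8 − 1 = 7. In Cycle 1, where nivolumab is given on Day 3, 8 − 3 = 5.
- A progression scan used as the termination visit. The Week 8 scan (Day 57) has a window of ±1 week, so it may fall on Day 50. The preceding dose is on Day 43, and 50 − 43 = 7.

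**Range of collection ends.** Under Section 7 and the synopsis, t runs from 0 to 30, so collection ends between Day 90 and Day 120. Note x counts its 30 days from meeting a discontinuation criterion, which may come after a dose hold. If a 28-day hold is counted from the last dose (an assumption), t = 28 + 30 = 58 and collection ends on Day 148. Section 7 would not allow that visit date, so the two rules conflict.

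**What else is scheduled?**

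- The termination visit itself (Day 0 to 30 under Section 7).
- The 4-week post-termination PK/ADA visit in Table 3, for Phase 1b subjects, at about day t + 28 (Day 28 to 58).
- The first 3-monthly follow-up contact. If counted as 91 days from the termination visit (an assumption), it falls on day t + 91 (Day 91 to 121), about one day after collection closes. Its stated purpose is survival and subsequent therapy.

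In the readable text, no contact after the termination visit has both a stated day and an AE query. The Schedule's AE row is drawn as an arrow whose right-hand end cannot be read, so this is a statement about the text only.

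**The case against.** The strongest reply is that the gap is short, partly covered and of unknown frequency. Much of that stands.

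- **Short.** It is at most 10 days, and zero once the termination visit is 10 or more days after the last dose, for example at the next 14-day dosing visit. Under the main TEAE definition, starting another treatment closes the window early anyway.
- **Partly covered.** SAEs and immune-related AEs already reported are followed to resolution or stabilization (Section 8.3.1.3). A related SAE that the investigator learns of is reportable at any time. These rules do not reach new non-serious events or SAEs judged unrelated, and Section 8.3.1.1 does not oblige investigators to seek events in former subjects.
- **Little effect on some tables.** The SAP counts each preferred term once per subject, and every subject in the earlier study had at least one TEAE (Section 1.2). The overall TEAE percentage could hardly move.

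Three stronger readings are tempting, and the documents do not support them:

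1. A reader might infer that no safety contact falls within the 100 days. The termination visit normally does, with examination, laboratory tests and ECG. The Table 3 visit also exists, and subjects who stop before confirmed progression continue planned assessments (Section 4.2).
2. A reader might infer that the loss is specific to subjects who stop for toxicity. It depends only on t. A progression stop can lose the same days, and a toxicity stop after a hold may have the longest collection.
3. A reader might infer that event percentages are biased low in that group. The documents give no event rate for Days 91 to 100 and do not tie the gap to that group. The SAP sets a limit on onset date and does not claim complete observation to Day 100.

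**Conclusion.** The rule is wrong as written: the collection requirement does not always cover the window that the safety tables use. For a termination visit 0 to 9 days after last dose, 10 to 1 days of the 100 have no collection requirement, whatever the reason for stopping. The events exposed are new-onset non-serious AEs and AESIs, and SAEs judged unrelated. Collection beyond Day 100, when t exceeds 10, takes nothing from the TEAE analysis.

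The size in days follows from the two stated rules alone. The number of subjects affected and the number of events missed cannot be derived from the documents, and the effect is probably small. Collection ends on Day 90 to 120 under Section 7 and the synopsis. Later ends arise only if note x governs, and these passages contradict each other. The safety follow-up named in Section 4.2 has no dated, AE-specific contact after the termination visit in the readable text.

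**What to change.** 1. In Section 8.3.1.1 and Schedule note m, and in the matching medication window of Section 4.6, collect until the later of 90 days after the termination visit and 100 days after the last dose of either drug. This also gives a defined end where no termination visit takes place.
2. Reconcile Section 7, the synopsis and note x so that the termination visit has one anchor. The choice is the sponsor's.
3. Add an AE, SAE and AESI query to an existing follow-up contact on or after Day 100 from last dose, so that the safety follow-up in Section 4.2 has a dated content.
4. In the SAP, report by cohort the number of subjects whose AE ascertainment ended before Day 100 for reasons other than death or new therapy. SAP Section 6.3 says that the study was terminated, so items 1 to 3 may reach few or no subjects. This item remains useful regardless.

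**Cost.** Protocol wording, one added query at an existing contact (possibly moved by some days), and one line in the disposition or AE table. The downside is up to 10 more days of AE collection in some subjects.
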